9.3. Safety Analyses

Adverse events will be coded using the standard dictionary (MedDRA) down to the lower level term (LLT).

An overall summary table will be presented (Any adverse event, any treatment emergent adverse event (TEAE), any serious adverse event (SAE), death, any grade 3 or higher adverse events from baseline to the end of Study. This analysis will be conducted on SAF population.

Two periods will be defined for TEAE:

- Any adverse event which occurs or worsens from first dosing to Day 56;
- Any adverse event which occurs after Day 56.

Adverse events will be described by primary system organ class and preferred term. Numbers and percentage of subjects, and number of occurrence of adverse event will be presented for:

- TEAE:
- Serious TEAE;
- TEAE leading to drug discontinuation;
- TEAE of grade 3 or 4;
- TEAE for which relationship with the study drug is recorded as possible or probable.

Analysis of safety will be performed on the safety data set consisting all subjects who received at least one dose of ABX464 in the study.

Primary safety endpoint, the rate of all treatment emergent adverse experiences will be compared between the study groups by stratified likelihood ratio chi-square test on a 10% one-sided significance level.

Further assessment of safety will be based on the frequency of adverse events (with and without regard to causality) graded according to the CTC-AE Classification and also, the review of individual values for clinical laboratory data, vital signs and ECG focusing on the detection of abnormal values and PCSAs [potentially clinically significant abnormalities (PCSAs) determined upon investigator considerations].

Adverse events will be tabulated (counts and percents) by group. All adverse events will be listed and the data will be tabulated by body system/organ class. Adverse event tabulations will include all treatment emergent adverse events, which will be further classified by severity, and relationship to treatment and dose level.

Clinical laboratory parameters, vital signs, ECG will be summarized by using descriptive statistics (n, mean, SD, SEM, median, minimum and maximum). Number of subjects with at least one abnormal values will be tabulated (counts and percents) for each parameter in summary shift tables, by group and dose.

9.3.1. Clinical laboratory evaluation

Descriptive statistics for laboratory parameters will be computed at each scheduled assessment. If relevant for some parameter, change from baseline will also be tabulated.

In addition, shift tables from baseline will be presented.

9.4. Determination of Sample Size

The primary efficacy endpoint is the rate of subjects responding to treatment. This response rate will be compared in subjects who received ABX464 or placebo by likelihood ratio chi-square test. For the sample size assessment, the following assumptions will be made:

- Response rate (ABX464): 0.6
- Response rate (placebo): 0.2

According to literature the response rate for ABX464 treated subjects is expected to be between 50% and 75% while that in the placebo group is assumed to be approximately 10% to 20% (Gemini 1 study - N Engl J Med 2013; 369:699-710 August 22, 2013).

- Type 1 error: 10% one-sided
- Group allocation rate (ABX464 / placebo): 2:1

If the above assumptions and definitions hold true with a sample size of 30 subjects receiving ABX 464 or placebo in a ratio of 2:1 the study has 81% power to show a difference in response rate between the study groups. To gain more clinical experience with ABX464 in this indication a 2:1 randomization ratio was chosen despite the inevitable loss of power. The actual loss of power with the above assumptions is 4%. Power was computed using the normal approximation method.

Subjects who terminates the study prematurely will be considered failures therefore no adjustment for dropouts is needed.

Primary safety endpoint is the rate of all treatment emergent adverse experiences. The above sample size is sufficient to detect an increase in general treatment emergent adverse experience rate from 10% to 50% with 86% power by likelihood ratio chi-square test on a 10%, one-sided significance level.

If approximately 20 subjects receive ABX464 the study has 88% chance to detect at least 1 specific treatment emergent AE if the underlying rate of occurrence is 1:10.

When the underlying rate of occurrence is around 1:20 the sample size of 20 subjects is sufficient to observe at least 1 such an event with a probability of 64% in the active treatment group.

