9.2. Efficacy Analysis

Analysis of efficacy data will be carried out in the Full Analysis Set in which subjects who prematurely terminate the study will be considered failures.

The primary efficacy endpoint of the study, the rate of subjects responding to treatment. This response rate will be compared in subjects who received ABX464 or placebo by stratified likelihood ratio chi-square test on a 10% one-sided level.

In addition, descriptive statistics will be presented by treatment arm for all secondary efficacy variables for each measurement timepoints separately for the two study groups.

These statistics include:

- Continuous variables: mean, standard deviation, minimum and maximum, stratified 95% confidence intervals, median and quartiles will be presented.
- Categorical variables: counts, rates and stratified 95% confidence intervals for the rates will be calculated.

In addition to descriptive statistics, the following analyses will also be carried out for the variables indicated below:

- Kaplan-Meier estimates and plots will be presented for time to UC worsening after week 8.
- Mixed model analysis of covariance will be conducted for the following measurements:
 - O The change from screening in IL-22 expression levels in serum and rectal/sigmoidal tissue at week 8,
 - O The change from baseline in microRNA-124 levels in whole blood (PAXgene®) and in tissue (RNA later) at week 4 and week 8,
 - O The change from baseline in fecal calprotectin levels at week 4 and week 8,
 - O The change from screening in the histopathology/infiltrate (rectal/sigmoidal biopsies) assessed by the Geboes score at week 8,

In this model, treatments and stratum will be fixed effects, subjects will be random effect and baseline values of the respective measurements will be covariates. Other explanatory variables will also be allowed to be included in the model. In order to normalize eventual skewed distributions transformation of the data will also be considered. Study groups will be compared within this model framework. All p-values will be interpreted in a descriptive manner.

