3.5 SAMPLE SIZE CONSIDERATIONS

The primary efficacy endpoint is the rate of subjects responding to treatment. This response rate will be compared in subjects who received ABX464 or placebo by likelihood ratio chi-squared test. For the sample size assessment, the following assumptions will be made:

Response rate for ABX464: 0.6

• Response rate for placebo: 0.2

According to literature, the response rate for ABX464 treated subjects is expected to be between 50% and 75% while that in the placebo group is assumed to be approximately 10% to 20%.

The Type I error is defined to be one-sided 10% significance level, and the group allocation rate is 2:1 (ABX464/ placebo). If the above assumptions and these definitions hold true with a sample size of 30 subjects receiving ABX464 or placebo in a ratio of 2:1, then the study has 81% power to show a difference in response rate between the treatment groups. Power was computed using the normal approximation method. A 2:1 randomisation ratio was chosen to gain more clinical experience with ABX464 in this indication, despite the inevitable loss of power. The actual loss of power with the above assumptions is 4%.

Subjects who terminate the study prematurely will be considered failures, therefore no adjustment for dropouts is needed.

The primary safety endpoint is the rate of all treatment emergent adverse events. The above sample size is sufficient to detect an increase in general treatment emergent adverse event rate from 10% to 50% with 86% power by likelihood ratio chi-squared test at a one-sided 10% significance level.

If approximately 20 subjects receive ABX464, the study has 88% chance to detect at least I specific treatment emergent adverse event if the underlying rate of occurrence is 1:10. When the underlying rate of occurrence is around 1:20 the sample size of 20 subjects is sufficient to observe at least I such an event with a probability of 64% in the active treatment group.

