6.1 FULL ANALYSIS SET

The Full Analysis Set (FAS) is defined as those patients who have received at least one dose of the study treatment, and who have at least one baseline value.

The FAS will be used for primary analyses. Patients who receive the wrong treatment in error will be analysed as randomised for efficacy analyses.

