6.3 PER PROTOCOL SET

The Per Protocol (PP) set is defined as those patients of the FAS population without any major protocol deviation and who completed the study (D56).

The PP set will be used for all efficacy analyses.

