11.3 EFFICACY ANALYSES

Treatment comparisons will be ABX464 vs placebo. The main analysis set for the efficacy analyses will be the PP, and the primary analysis will be repeated for the FAS Set.

Subjects who prematurely terminate the study will be considered failures.

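### The reason given for making no dropout allowance fits the FAS, but the SAP's main efficacy analysis uses a completers-only per-protocol set in which that reason cannot apply

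*Protocol*

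**What the plan says.** **Sample size.** Protocol 9.4 and SAP 3.5 assume rates of 0.6 on ABX464 and 0.2 on placebo, 2:1 allocation, 30 subjects and a one-sided 10% level. SAP 3.5 concludes that "the study has 81% power to show a difference in response rate between the treatment groups". Neither document makes a dropout allowance. Protocol 9.4 gives the reason: "Subjects who terminates the study prematurely will be considered failures therefore no adjustment for dropouts is needed". SAP 3.5 repeats it.

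**Analysis set, version A (FAS).** Protocol 9.2 has efficacy "carried out in the Full Analysis Set in which subjects who prematurely terminate the study will be considered failures". SAP 6.1 agrees: "The FAS will be used for primary analyses". SAP 6.2 assigns all safety analyses to the Safety Set, so the primary efficacy analysis is the natural reading of that sentence.

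**Analysis set, version B (PP).** SAP 11.3 states: "The main analysis set for the efficacy analyses will be the PP, and the primary analysis will be repeated for the FAS Set". SAP 11.3.1 and the SAP table list follow this: remission is tested on the PP first and on the FAS second, and every other efficacy table is PP only. SAP 6.3 defines the PP as FAS patients "without any major protocol deviation and who completed the study (D56"). The completion condition is not in the PP definition of Protocol 9.1.2. SAP 11.3 then adds: "Subjects who prematurely terminate the study will be considered failures".

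**Replacement.** Protocol 7.2 and SAP 3.6 replace a subject who leaves early for a reason unrelated to the drug. The replacement takes the next allocation, which may be to the other arm.

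**The concern.** Counting an early terminator as a failure requires that the subject remains in the analysis. A set restricted to Day 56 completers contains no early terminators, so in the SAP's main efficacy analysis the failure rule has nothing to act on. Two consequences follow.

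- **Bias.** The main remission comparison excludes patients for something that happens after randomisation. Worsening of UC is one of the withdrawal reasons in Protocol 7.2, so a subject withdrawn for worsening would drop out of the main analysis when the protocol would count that subject as a failure.
- **Power.** The 81% is the efficacy justification for 30 subjects and will be used to interpret a non-significant remission result. It was worked out for 20 and 10 subjects all counted. It does not carry over to a smaller, selected set.

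A smaller point concerns the endpoint. The sample size text speaks only of a *response rate*, the primary efficacy endpoint is clinical remission, and SAP 4.2.2 defines a separate *clinical response*.

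**Working it through.** **Inputs.** p1 = 0.60, p2 = 0.20, n1 = 20, n2 = 10, one-sided 10% (z = 1.2816), normal approximation (Protocol 9.4, SAP 3.5). The documents give no dropout or PP-exclusion rate, so 10% and 20%, equal in both arms, are assumptions.

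**Formula.** Power = Φ[(|p1 − p2| − z·s0)/s1], where s0 = √[p̄(1 − p̄)(1/n1 + 1/n2)], s1 = √[p1(1 − p1)/n1 + p2(1 − p2)/n2], and p̄ is the weighted mean rate.

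**Step 1: the plan's figure.** p̄ = (12 + 2)/30 = 0.4667. s0 = √(0.4667 × 0.5333 × 0.15) = 0.1932. s1 = √(0.012 + 0.016) = 0.1673. Power = Φ[(0.40 − 0.2476)/0.1673] = Φ(0.911) = 81.9%, against the stated 81%. With 15:15 the result is 85.2%, a loss of 3.3 points from 2:1 allocation, against the stated 4%. The arithmetic holds.

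**Step 2: what the 60% and 20% could mean.** The plan does not say whether they are rates among completers or rates with dropouts already counted as failures. With dropout d:

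- If they are completer rates, the FAS rates are 0.60(1 − d) and 0.20(1 − d), and the PP rates are unchanged.
- If they already count dropouts as failures, the FAS rates are unchanged, and the PP rates are 0.60/(1 − d) and 0.20/(1 − d).

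**Step 3: replacement.** The two limits are no replacement, and replacement of every dropout in the same 2:1 ratio. The second returns the PP to 20:10 and enlarges the FAS to 20/(1 − d) and 10/(1 − d).

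| Set | Meaning of 60%/20% | Replacement | d = 10% | d = 20% |
|---|---|---|---|---|
| PP | completer rates | none | 18:9, 0.60/0.20: 78% | 16:8, 0.60/0.20: 74% |
| PP | completer rates | full | 20:10, 0.60/0.20: 82% | 20:10, 0.60/0.20: 82% |
| FAS | completer rates | none | 20:10, 0.54/0.18: 76% | 20:10, 0.48/0.16: 69% |
| FAS | completer rates | full | 22.2:11.1, 0.54/0.18: 79% | 25:12.5, 0.48/0.16: 77% |
| PP | dropouts counted as failures | none | 18:9, 0.667/0.222: 85% | 16:8, 0.75/0.25: 89% |
| FAS | dropouts counted as failures | none | 20:10, 0.60/0.20: 82% | 20:10, 0.60/0.20: 82% |

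The PP rows allow for dropout only. Excluding a further assumed 10% of completers for major deviations, with 10% dropout and no replacement, leaves 20 × 0.9 × 0.9 = 16.2 and 8.1. Power at 0.60/0.20 is then 75%.

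**Step 4: reading the table.** Even in the FAS, the dropout sentence preserves about 82% without replacement only if 60%/20% already count dropouts as failures. In the PP, power can move either way, and the plan does not let a reader say which.

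**The case against.** The strongest reply has four parts.

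- **Replacement.** Non-drug-related exits are replaced, so figures that ignore this overstate the loss. This stands, and for that reason the table shows both limits. It does not rescue the sentence. Drug-related exits are not replaced, subjects with major deviations who stay in the study are lost to the PP without having exited, and a replacement may go to the other arm. Nor is replacement the reason that Protocol 9.4 and SAP 3.5 give.
- **The FAS analysis is there.** Remission is also tested on the FAS (SAP Table 14.2.1.2), where the failure rule works. True, but the SAP labels it as the repeat.
- **Limited consequence.** The primary endpoint is safety, the trial is a 30-subject proof of concept, and the SAP (23 August 2018) postdates the planned end of recruitment (Q2 2018). This stands: the point bears on how efficacy is read, not on the sample size or the validity of the trial.
- **The endpoint is identifiable.** A reader might infer that 60%/20% are not remission rates at all. The documents do not support that. Protocol 9.4 and SAP 3.5 attach the rates to the primary efficacy endpoint, Protocol 2.4 and SAP 4.2.1 define that endpoint as week-8 clinical remission, and SAP 11.3.1 and the remission table footnote call the remission proportion a response rate. The identification is indirect, and the separate clinical response endpoint makes it easy to misread. That is a wording point. Whether the cited literature range concerns remission or response cannot be checked from the documents.

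**Conclusion.** The concern holds as an inconsistency between analysis sets. The dropout reasoning in Protocol 9.4 and SAP 3.5 agrees with Protocol 9.2 and SAP 6.1. It cannot apply to the main efficacy analysis in SAP 11.3 and 11.3.1, given the PP definition in SAP 6.3. The SAP also contradicts itself on which set is primary.

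Two stronger readings are tempting and fail. One is that 81% is a miscalculation; it reproduces. The other is that the trial is underpowered and should have enrolled more. Under the assumed 10% or 20% equal dropout, PP power runs from 74% to about 82% if 60%/20% are completer rates, depending on replacement. It is 85% or 89% without replacement if they already count dropouts as failures. With no dropout rate in the plan and no statement of what the rates include, no definite shortfall from 81% is shown.

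The more important consequence is that the main remission comparison is open to selection after randomisation, which the protocol's own FAS rule would avoid. This should be fixed, and it affects the interpretation of efficacy only.

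**What to change.** All changes should be dated before database lock and unblinding; SAP 9.3 loads the randomisation list only after lock.

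1. Amend SAP 6.3, 11.3, 11.3.1 and the table list so that the FAS, with premature terminators counted as failures, is the main efficacy set and the PP is the supportive repeat. This restores agreement with Protocol 9.2 and SAP 6.1.
2. In Protocol 9.4 and SAP 3.5, name the endpoint as week-8 clinical remission and say whether 60% and 20% count non-completers as failures.
3. If they do, keep the 81% and the dropout sentence. If they do not, drop the sentence and restate the power for the FAS, taking the replacement rule into account.

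The cost is text only: the sample size and the test stay as they are. The downside is that the stated power may become slightly less favourable. If 60%/20% are completer rates, the FAS figure would be about 79% at 10% dropout or 77% at 20% with full same-ratio replacement, and 76% or 69% with none (dropout rates assumed).

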10. STUDY CONDUCT CONSIDERATION

10.1. Regulatory and Ethical Considerations

10.1.1. General Requirements

The study will be conducted in compliance with the study protocol, ABIVAX / SIMBEC-ORION Standard Operating Procedures and in accordance with any local regulatory requirements, to ensure adherence to Good Clinical Practice (GCP) as described in the following documents:

- ICH Harmonized Tripartite Guidelines for Good Clinical Practice 1996.
- US 21 Code of Federal Regulations dealing with clinical studies (including parts 50 and 56 concerning informed consent and IRB regulations).
- Directive 2001/20/EC on the approximation of the laws, regulations and administrative provisions of the Member States relating to the implementation of good clinical practice in the conduct of clinical studies on medicinal products for human use and its guidance.
- Declaration of Helsinki and its amendments.

Upon signing the protocol, the investigator agrees to adhere to the instructions and procedures described in it and thereby to adhere to the principles of Good Clinical Practice that it conforms to.

Written informed consents will be obtained for each subject before he or she can participate in the study.

ABIVAX will obtain favorable opinion/approval to conduct the study from the appropriate regulatory agencies in accordance with any applicable country-specific regulatory requirements prior to a site initiating the study in that country.

10.1.2. Independent Ethics Committee/Institutional Review Board

Prior to the start of the study, the study protocol and amendments if applicable as well as other appropriate study-related documents will be submitted to an independent Institutional Review Board (IRB) or independent Ethics Committee (IEC), respectively.

For each center it will be individually specified, who (investigator or sponsor) will be responsible for informing the IRB or IEC, respectively of any protocol amendments or new relevant information that require an ethical reconsideration of the study protocol.

If the investigator is responsible for obtaining approval, he/she should also obtain a statement from the IRB or IEC, respectively that it is organized and operates according to GCP and applicable laws and regulations.

10.1.3. Subject Informed Consent

It is the responsibility of the investigator to give each subject full and adequate verbal and written information regarding the aims, methods, anticipated benefits and potential hazards. The subject must be informed that participation is voluntary, and that they are free to withdraw from the study at any time without any disadvantages for their subsequent care. Although a subject is not obliged to give her/his reason(s) for withdrawing prematurely from the trial, the investigator should make a reasonable effort to ascertain the reason(s), while fully respecting the subject's rights. Written consent (signed and dated by the subject and the investigator) must be obtained prior to admission. The subject must be provided with a copy of the subject information and informed consent.

The data collected in this study will be processed anonymously at ABIVAX. Subjects should be informed about the purpose of the planned computer data processing and the publication of the data (e.g. at scientific meetings). The subject must give consent to the computer processing and to the publishing of anonymous data.

The subject must be informed of and consent in writing that personal data relating to the trial may be subject to audits by Health Authorities and the sponsor. However, personal data will be kept strictly confidential and will not be made publicly available.

10.1.4. Compensation to Subjects

Insurance coverage will be provided for all subjects enrolled in the study from the time of the subject's inclusion in the study (i.e. date of signing the ICF). The insurance coverage will be provided by the Sponsor and will be in line with GCP guidance and legal requirements, but also in accordance with local regulations. A confirmation of insurance and corresponding insurance conditions should be archived in the Investigator File.

Besides, due to the cumbersome procedures related to the study (number of visits, sigmoidoscopies...) subjects could be financially compensated by the Sponsor in accordance with the national regulations and the approval of the Ethics Committees.

11. STUDY MANAGEMENT

11.1. Remote Data Entry

An electronic case report form (eCRF) will be used to record all data required by the protocol. Remote Data Entry (RDE) will be used for data collection, *i.e.* the subject's information pertaining to the study, will be entered into the eCRF via a computer at the investigational site.

Prior to the start of the study, the investigator will complete a "Investigator site staff signatutre and task delegation log" form, showing the signatures and initials of any person who is authorized to make or change entries in the eCRF and any person authorized to electronically sign the eCRF.

The eCRF used for this study is validated and fulfils the International Conference on Harmonization (ICH) Good Clinical Practice (GCP) requirements, European and FDA (21 CFR Part 11) regulations.

Training sessions will be held for all the participants who will use this tool (e.g. investigators, ABIVAX staff and contract research organization [CRO] staff, including project managers, CRAs and data managers).

Several supports are available to help all users with this tool including eCRF User Guide and five days a week / working hours helpdesk (support line).

All of the information will be recorded through transcription from source documents into the eCRF by an authorized person.

The investigator is responsible for the management and accuracy of the information in the eCRF. At each monitoring visit, the subject medical files should be at the clinical research associate's (CRA) disposal for review.

